11.2 Study participation

11.2.1 Information

No examinations will be carried out before the patient concerned gave his/her written informed consent. Before any study-related trial procedures, the investigator will:

- Explain the nature, purpose and potential risks of the trial in which patients volunteer to participate and answer all questions regarding this trial,
- Inform patients that their participation is voluntary and that they may withdraw consent to participate at any time without giving any reason; if patients decide not to participate or withdraw from the trial, it will not affect the standard care they will receive to treat their disease,
- Provide to patients the informed consent form in their own language. The patients will be given sufficient time to consider before consenting,

The investigator(s) has both ethical and legal responsibility to ensure that each patient being considered for inclusion in this trial is given a full explanation of the protocol.

11.2.2 Obtaining consent

Once the appropriate essential information has been provided to the patient and fully explained by the investigator (or a qualified designee) and it is felt that the patient understands the implications of participating, the IRB (Institutional Review Board)/IEC-approved written informed consent form shall be signed and dated by both the patient and the person obtaining consent (investigator or designee), and by any other parties required by the IRB/IEC. The patient shall be given a copy of the signed informed consent form; the original shall be kept on file by the investigator. All of the above mentioned activities must be completed prior to the patient's participating in the trial.

After obtaining the informed consent form signed and personally dated by the patients, the investigator must attribute a trial identification code to any patient who has accepted to participate into the trial (see procedure described below).

The inclusion and non-inclusion criteria after signature of the written informed consent must be checked.

Patients that fail screening may be re-screened while keeping their previous identification code.

11.2.3 Patient identification

The investigator will assign an identification code to the patient according to the following procedure.

The patient identification code is composed of:

- Two letters for the country: FR for France, ES for Spain
- The centre number (3 digits)
- The patient order of entry in the trial in this centre (3 digits)
- A four letter code randomly generated and be provided to any participant centres by the CMG Inserm UMR S 1136 before starting the trial

For example, for a patient, screened in France, in centre 060, and screened for inclusion at the second position in this centre with letter code of FRSD, the patient identification code will be: FR-060-002-FRSD.

11.3 Screening visit (W -6/W-4)

This visit will be performed between 4 and 6 weeks before the beginning of trial treatment (RAL/ETR) at D0 Visit.

During this visit, the investigator:

- Collects the fully informed patient's consent,
- Collects the following patient characteristics (Birth date, Sex, Origin and HIV transmission group) and patient's lifestyle (tobacco, drugs and alcohol),
- Collects current/previous ART,

- Interviews the patient to collect the medical history, the potential concomitant pathologies and concomitants treatments,
- Evaluates the patient's adherence using self-questionnaires
- Performs an extensive and detailed anamnesis of the patient's immunovirologic history including a complete chronological list of the viral strains genotypes allowing the exclusion of any virological failure under NNRTI treatment. In addition, the investigator has to perform prior to inclusion a Genotypic resistance on blood DNA showing its full sensibility to ETR and RAL,
- Performs a clinical examination: blood pressure, heart rate, body temperature, targeted physical examination, weight, and height. An ECG will be performed to exclude any concomitant condition that might jeopardize patient's safety and participation,
- Performs urinary pregnancy test for women of childbearing potential,
- Collects urine sample for urine analysis: proteinuria, albuminuria, creatininuria, glycosuria,
- Collects blood samples for the following biological exams:
 - Whole blood cells counts
 - HIV-RNA plasma viral load
 - Genotypic resistance on blood DNA
 - CD4/CD8 lymphocytes count
 - Creatinine, CPK, AST, ALT and bilirubin dosages
 - HBV and HCV serologies
 - β HCG for women of childbearing potential with positive urinary test

A copy of the biological exams with an anonymized copy of the Patient's Informed Consent Form will be faxed by the investigator to CMG Inserm UMR S 1136 in order for them to validate the inclusion.

The investigator will schedule the D0 visit and the DXA scan of D0 visit (for patients participating in the DXA sub-study). DXA scan might be performed with a time limit up to 7 days before the date of D0 visit.

11.4 Day 0 visit (inclusion)

The designated D0 Visit (Day 0) is the date planned for the first prescription and, a fortiori, the first administration of trial treatment (RAL/ETR).

During this visit, the investigator:

- Realizes a clinical examination (blood pressure, heart rate, body temperature, targeted physical examination, weight) and anthropometric measurements (specific circumferences: abdomen (perimeter at the umbilicus) and hips (bi-trochanterian perimeter)). Cardiovascular risk factors (arterial hypertension, tobacco, alcohol abuse, physical activity, diabetes) and the measurement of the systolic blood pressure (refer to appendix 7) will be recorded.
- Checks the presence of intercurrent pathologies and the treatments intake
- Evaluates the patient's quality of life and felt symptoms using self-questionnaires
- Performs urinary pregnancy test for women of childbearing potential, in case of suspicion
- Collects blood samples for the following biological exams:
 - HIV-RNA plasma viral load
 - CD4/CD8 lymphocytes count
 - Lipids (fasting triglycerides, total cholesterol, HDL-Cholesterol, and LDL-cholesterol) and fasting glycemia
 - Sample bank (plasma, serum and whole blood bank)
- DXA-Scan will be performed for patients participating in this sub-study (DXA scan might be performed up to 7 days before D0 visit).

A copy of the biological exams will be faxed by the investigator to CMG Inserm UMR S 1136.

The investigator will give the first prescription of trial treatment (RAL/ETR) and schedule the W2 visit.

11.5 Follow-up visits

After the D0 visit, 9 visits are scheduled in the clinical centres, W2, W4, W12, W24, W36, W48, W64, W80 and W96 or End of treatment (EOT). EOT visit will be performed in case of giving up or premature stop of trial

treatment. Assessments and procedures will be performed according to schedules reported in the table (schedule of assessment). A copy of all biological exams will be faxed by the investigator to CMG Inserm UMR S 1136.

11.5.1 Visits W2 to W80

- **W2 Visit:** the investigator will realize a clinical examination (blood pressure, heart rate, body temperature, targeted physical examination, weight), check the presence of intercurrent pathologies and the treatments intake. Urinary pregnancy test for women of childbearing potential will be performed, in case of suspicion. Blood samples will be collected for sample bank (plasma bank).
The investigator will schedule the W4 visit.
- **W4 Visit:** the investigator will realize a clinical examination (blood pressure, heart rate, body temperature, targeted physical examination, weight), check the presence of intercurrent pathologies and the treatments intake. Urinary pregnancy test for women of childbearing potential will be performed, in case of suspicion. Plasma HIV-1 RNA viral load, Creatinine, CPK, AST, ALT and bilirubin dosages will be realized in the local laboratory. Blood samples will be collected for sample bank (plasma bank). Urine sample for proteinuria, albuminuria, creatininuria, glycosuria analysis (in the local laboratory) will be collected.
The investigator will give the prescription of trial treatment (RAL/ETR) and schedule the W12 visit.
- **W12 Visit:** the investigator will realize a clinical examination (blood pressure, heart rate, body temperature, targeted physical examination, weight), check the presence of intercurrent pathologies and the treatments intake. Urinary pregnancy test for women of childbearing potential will be performed, in case of suspicion. Plasma HIV-1 RNA viral load, CD4/CD8 count, metabolic parameters (fasting triglycerides, total cholesterol, HDL-Cholesterol, and LDL-cholesterol), fasting glycemia, Creatinine, CPK, AST, ALT and bilirubin dosages will be realized in the local laboratory. Urine sample for proteinuria, albuminuria, creatininuria, glycosuria analysis (in the local laboratory) will be collected. Blood samples will be collected for sample bank (plasma bank).
The investigator will give the prescription of trial treatment (RAL/ETR) and schedule the W24 visit.
- **W24 Visit:** the investigator will realize a clinical examination (blood pressure, heart rate, body temperature, targeted physical examination, weight), check the presence of intercurrent pathologies and the treatments intake. Urinary pregnancy test for women of childbearing potential will be performed, in case of suspicion. Plasma HIV-1 RNA viral load, CD4/CD8 count, whole blood cells count, metabolic parameters (fasting triglycerides, total cholesterol, HDL-Cholesterol, and LDL-cholesterol), fasting glycemia, Creatinine, CPK, AST, ALT, bilirubin dosages and urine analysis (proteinuria, albuminuria, creatininuria, glycosuria) will be realized in the local laboratory. Blood samples will be collected for sample bank (plasma bank). The investigator will give the prescription of trial treatment (RAL/ETR) and schedule the W36 visit.
- **W36 Visit:** the investigator will realize a clinical examination (blood pressure, heart rate, body temperature, targeted physical examination, weight), check the presence of intercurrent pathologies and the treatments intake. Urinary pregnancy test for women of childbearing potential will be performed, in case of suspicion. Plasma HIV-1 RNA viral load will be realized in the local laboratory. Blood samples will be collected for sample bank (plasma bank).
The investigator will give the prescription of trial treatment (RAL/ETR), schedule the W48 visit and the DXA scan (for patients participating in the DXA sub-study). DXA scan might be performed with a time limit up to 10 days before and after the visit date of W48.
The investigator will deliver the dedicated container for patients participating in the seminal sub-study to collect the sperm within the 6 hours prior the W48 visit.
- **W48 Visit:** the investigator will realize a clinical examination (blood pressure, heart rate, body temperature, targeted physical examination, weight) check the presence of intercurrent pathologies and the treatments intake. Anthropometric measurements (specific circumferences: abdomen (perimeter at the umbilicus) and hips (bi-trochanterian perimeter)), cardiovascular risk factors (arterial hypertension, tobacco, alcohol abuse, physical activity, diabetes), measurement of the systolic blood pressure (refer to appendix 7) will be recorded. Urinary pregnancy test for women of childbearing potential will be performed, in case of suspicion. Plasma HIV-1 RNA viral load, CD4/CD8 count, whole blood cells count, metabolic parameters (fasting triglycerides, total cholesterol, HDL-Cholesterol, and LDL-cholesterol), fasting glycemia, Creatinine, CPK, AST, ALT, bilirubin dosages, urine analysis (proteinuria, albuminuria, creatininuria, glycosuria) will be realized in the local laboratory. Blood samples will be collected for sample bank (plasma, serum and whole

blood bank), The patient's quality of life, felt symptoms, and adherence will be collected using self-questionnaires.

Patients participating to the DXA-Scan sub-study will perform their second scans. DXA scan might be performed with a time limit up to 10 days before and after the visit date of W48.

At W48, patients participating to the seminal sub-study will bring the total sperm sample collected within the 6 hours prior the visit using the dedicated container delivered by the investigator at W36.

The investigator will give the prescription of trial treatment (RAL/ETR) and schedule the W64 visit.

- **W64 Visit:** the investigator will realize a clinical examination (blood pressure, heart rate, body temperature, targeted physical examination, weight), check the presence of intercurrent pathologies and the treatments intake. Urinary pregnancy test for women of childbearing potential will be performed, in case of suspicion. Plasma HIV-1 RNA viral will be realized in the local laboratory. Blood samples will be collected for sample bank (plasma bank).

The investigator will give the prescription of trial treatment (RAL/ETR) and schedule the W80 visit.

- **W80 Visit:** the investigator will realize a clinical examination (blood pressure, heart rate, body temperature, targeted physical examination, weight), check the presence of intercurrent pathologies and the treatments intake. Urinary pregnancy test for women of childbearing potential will be performed, in case of suspicion. Plasma HIV-1 RNA viral load, CD4/CD8 count, whole blood cells count, Creatinine, CPK, AST, ALT, bilirubin dosages and urine analysis (proteinuria, albuminuria, creatininuria, glycosuria) will be realized in the local laboratory. Blood samples will be collected for sample bank (plasma bank).

The investigator will give the prescription of trial treatment (RAL/ETR), schedule the W96 visit and the DXA scan (for patients participating in the DXA sub-study). DXA scan might be performed with a time limit up to 10 days before and after the visit date of W96.

11.5.2 Last visit of follow-up

The last visit of follow-up for each patient will be the week 96 visit if the patient completes the trial or the EOT visit in case of giving up or premature stop. Patients who stop the trial treatment will continue to be followed according to the trial calendar until the week 96.

- **W96 Visit:** the investigator will realize a clinical examination (blood pressure, heart rate, body temperature, targeted physical examination, weight), anthropometric measurements (specific circumferences: abdomen (perimeter at the umbilicus) and hips (bi-trochanterian perimeter), check the presence of intercurrent pathologies and the treatments intake. Cardiovascular risk factors (arterial hypertension, tobacco, alcohol abuse, physical activity, diabetes) and the measurement of the systolic blood pressure (refer to appendix 7) will be recorded. Urinary pregnancy test for women of childbearing potential will be performed, in case of suspicion. Plasma HIV-1 RNA viral load, CD4/CD8 count, whole blood cells count, metabolic parameters (fasting triglycerides, total cholesterol, HDL-Cholesterol, and LDL-cholesterol), fasting glycemia, Creatinine, CPK, AST, ALT, bilirubin dosages, urine analysis (proteinuria, albuminuria, creatininuria, glycosuria) will be realized in the local laboratory. Blood samples will be collected for sample bank (plasma, serum and whole blood bank). The patient's quality of life, felt symptoms and adherence will be collected using self-questionnaires.

Patients participating to the DXA-Scan sub-study will perform their third scans. DXA scan might be performed with a time limit up to 10 days before and after the visit date of W96.

- **EOT Visit (End of treatment):** this visit will be realized only in case of giving up or premature stop of trial treatment.

At this visit, the investigator will realize a clinical examination (blood pressure, heart rate, body temperature, targeted physical examination, weight), anthropometric measurements (abdominal and waist circumference), check the presence of intercurrent pathologies and the treatments intake. Urinary pregnancy test for women of childbearing potential will be performed, in case of suspicion. Plasma HIV-1 RNA viral, CD4/CD8 count, whole blood cells count, metabolic parameters (fasting triglycerides, total cholesterol, HDL-Cholesterol, and LDL-cholesterol), fasting glycemia, Creatinine, CPK, AST, ALT, bilirubin dosages, and urine analysis (proteinuria, albuminuria, creatininuria, glycosuria) will be realized in the local laboratory. Blood samples will be collected for sample bank (plasma, serum and whole blood bank).

The patient's quality of life, felt symptoms and adherence will be collected using self-questionnaires.

11.6 Study end

The end of the trial occurs when the last patient still being followed realizes the week 96 visit, abandons or withdraws consent plus 6 months. At the end of the trial (six months after the last visit of the last patient), for each participant, according to the trial results, the investigator will decide to maintain or change the trial treatment. The patients will be followed with the best clinical practices. In case of premature stop of the trial, the investigator will follow the scientific committee recommendation. All patients will be informed of the trial results.

11.7 Premature and definitive stop of the study treatment

“Stop of treatment” is when the patient is not taking RAL and/or ETR.

All patients who discontinue trial medication will be followed up and requested to attend for trial visits up until week 96, even if they stop taking trial medication.

Reasons of a premature stop can be:

- Wish of the patient,
- Intolerance or occurrence of an adverse event,
- New or worsening of an intercurrent pathology,
- Death of the patient,
- Virological failure defined as two successive HIV-RNA plasma viral loads > 50 copies/mL within 2 to 4 weeks,
- Pregnancy,
- All medical event that induce an interruption of the treatment,
- Major violation of the protocol,
- Non- adherence of the treatment resulting in danger for the health of the patient,
- Necessity for the patient to be treated by a non-authorized treatment in the protocol,
- Motivated investigator's decision for any other reason than those listed above.

“Premature stop” is considered as a deviation to the protocol if it is not due to a reason cited above. Any event resulting in premature stop should be reported within the two working days of the decision to discontinue in the eCRF using the dedicated form. The reason and date of the treatment discontinuation will have to be documented. The CMG project manager will receive an automatic alert email. Patients who stop the trial treatment will continue to be followed according to the trial calendar.

The investigator must collect the information for the primary end points at the time of the premature stop of trial treatment (EOT visit).

11.8 Lost to follow-up

A patient is considered lost to follow-up when he/she is not coming to more than 2 consecutives visits of the protocol. Three documented attempts should be made to contact the patient via telephone and one registered letter (letter which requires signature upon receipt) should be sent to the patient prior to assigning the patient as lost to follow-up. Patients who cannot be contacted on or before the last scheduled visit prior to the week 96 and who do not have a known reason for discontinuation (eg, withdrew consent, giving up, etc.) will be classified as “lost to follow-up”.

The CMG UMR S 1136 should be informed as soon as possible using the dedicated form in the eCRF. The CMG project manager will receive an automatic alert email.

11.9 Withdrawal of the consent and giving up

Patients who want to giving up or withdraw their consent as they are allowed to do at any time, are no more followed in the context of the protocol but will be followed with the best clinical practices.

11.9.1 Consent withdrawal

In case of a withdrawal of the consent, the investigator must inform the CMG UMR S 1136 to have the procedure to follow. The patient's data will be removed (from the date of the consent's withdrawal) from the database according to the law (loi n°78-17 du 6 janvier 1978 modifiée, article 38) and the biological samples will be destroyed.

Any consent withdrawal has to be confirmed to the Methodology Centre by using the dedicated form in the eCRF within the two working days, and date of withdrawal.

Subjects withdrawing from the trial may be replaced if considered necessary by the Coordinating investigator.

11.9.2 Giving up

Patients give up the trial when they refuse to continue the follow-up of the trial. The investigator must identify the reason and collect the information for the primary end points at the time of the giving up (EOT visit). The CMG UMR S 1136 should be informed within the two working days using the dedicated form in the eCRF. The reason and date of discontinuation have to be documented. The CMG project manager will receive an automatic alert email.

They will be followed with the best clinical practices.

11.10 Protocol deviations

According to Good Clinical Practices sponsor and investigators should not use systems of prospectively approving protocol deviations, in order to effectively widen the scope of a protocol.

Protocol deviations have to be fully argued and documented. Are defined as major protocol deviations the following violations related to: regulatory aspects of the research, eligibility criteria, the primary evaluation criteria, the investigational treatment. The whole protocol deviations will be listed and submitted to both Trial Scientific Committee, Data Safety Monitoring Board and to the sponsor. According to the deviation, the end of participation of the patient concerned may be considered

11.11 Trial-specific rules for treatment management

11.11.1 Virological failure

A virological failure is defined as two consecutive HIV-RNA plasma viral loads > 50 copies/mL within an interval of two to four weeks. During the course of the trial, the onset of an HIV-RNA plasma VL > 50 copies/mL will automatically conduct to schedule an additional blood collection within an interval of two to four weeks to confirm the rebound of the HIV-RNA plasma VL. If the virological failure is confirmed, a resistance genotype and a dosage of ARV drugs concentration in plasma will be performed on the second HIV-RNA plasma VL test. A plasma bank should also be done.

- If the HIV-RNA plasma VL rebound is not confirmed by the second test, the trial treatment will be maintained without any specific adaptation.
- If the HIV-RNA plasma VL rebound is confirmed by the second test the baseline ARV regimen will be immediately reintroduced. If needed, treatment will be subsequently adapted according resistance genotype.

In order to ensure real-time virological safety for patients included, the Data Safety Monitoring Board will be informed every time 2 virological failures are confirmed by two consecutive plasma viral load tests > 50 copies/mL within 2 to 4 weeks. (see 10.2.2)

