Critères de jugement	
Critère principal
 
Proportion de patients en succès virologique jusqu'à S48 défini par l'absence de 2 CV ARN-VIH > 50 copies/mL mesurées dans un intervalle de 2 à 4 semaines maximum.
 
Les critères secondaires
 
•Efficacité biologique
 
 - Pourcentage de patients ayant maintenu le succès thérapeutique jusqu'à S48 et S96 défini par l'absence d'échec virologique (i.e. 2 CV consécutives >50 copies/mL mesurées dans un intervalle de 2 à 4 semaines maximum) et par l'absence d'arrêt du traitement de l'essai dû à la survenue d'un événement indésirable jugé par le comité indépendant de surveillance (CIS) comme lié au traitement ou à la stratégie de l'essai. - Pourcentage de patients en succès virologique (ARN-VIH ≤50 copies/mL) jusqu'à S96. - Pourcentage de patients ayant arrêté le traitement de l'essai. - Pourcentage de patients ayant une charge virale ARN-VIH entre 51 et 200 copies/mL et le pourcentage de patients ayant une charge virale ARN VIH >200 copies / mL au moment de l'échec virologique. - Délai médian entre la date de l'initiation du traitement de l'essai et la perte du succès virologique. - Pourcentage de patients avec des virus présentant des mutations de résistance au traitement de l'essai en cas d'échec virologique et pourcentage de patients avec des virus résistants à toutes les molécules de

la classe thérapeutique en cas d'échec virologique.

- Recherche de facteurs associés à la survenue d'une charge virale >50 copies/mL (historique des génotypes, charge virale pré-thérapeutique, concentration plasmatique des médicaments de l'essai (étravirine, raltégravir) mesurée au rebond virologique, le réservoir viral mesuré par l'ADN-VIH à J0 et l'observance mesurée par auto-questionnaire).
- Evolution de l'ADN-VIH total dans les cellules de J0, à S48 et à S96.
- Evolution des cellules lymphocytaires T CD4+ et T CD8+ et le rapport CD4/CD8 à tous les points de mesure par rapport à J0.

• *Tolérance et impact métabolique*

- Pourcentage de patients présentant au moins un événement indésirable grave jugé par le CIS comme liés au traitement ou à la stratégie de l'essai.
- Pourcentage de patients ayant eu des événements indésirables cliniques ou biologiques de grade 3 ou 4.
- Evolution des paramètres métaboliques mesurés à jeun (triglycérides, cholestérol total, HDL-cholestérol, LDL-cholestérol et glycémie).

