3 STUDY DESIGN

4 SCHEDULE OF ASSESSMENTS

	W-6/W-4	D0	W2	W4	W12	W24	W36	W48	W64	W80	W96	EOT
Informed Consent Signature	X											
Review eligibility criteria	X	X										
Collection of adverse events		X	X	X	X	X	X	X	X	X	X	X
Quality of life, felt symptoms		X						X			X	X
Adherence evaluation	X							X			X	X
Clinical exam (blood pressure, heart rate, body temperature, weight and targeted physical examination)	X ¹	X ^{2,3,4}	X	X	X	X	X	X ^{2,3,4}	X	X	X ^{2,3,4}	X ²
HBV/HCV serology	X											
Urinary pregnancy test If positive: β HCG ⁵	X	X ⁶	X ⁶	X ⁶	X ⁶	X ⁶	X ⁶	X ⁶	X ⁶	X ⁶	X ⁶	X ⁶
HIV-RNA plasma Viral Load⁷	X	X		X ⁸	X ⁸	X ⁸	X ⁸	X ⁸	X ⁸	X ⁸	X ⁸	X ⁸
CD4/CD8 Lymphocytes	X	X			X	X		X		X	X	X
Whole blood cells count	X					X		X		X	X	X
Creatinine, AST, ALT, CPK, bilirubin, urine analysis⁹	X			X	X	X		X		X	X	X
Lipid profile¹⁰, fasting glycemia		X			X	X		X			X	X
Genotypic resistance on blood DNA	X											
DXA-Scan sub-study¹¹		X						X			X	
Seminal sub-study¹²								X				
Study drug prescription		X		X	X	X	X	X	X	X		
Sample bank¹³												
Plasma bank: minimal plasma ARV concentration, virological analysis		X	X	X	X	X	X	X	X	X	X	X
Whole blood bank: Total cell-associated HIV-DNA		X						X			X	X
Plasma and serum bank: Immunologic analysis of inflammation markers¹⁴		X						X			X	X

¹ Electrocardiogram (ECG)

² Anthropometric measurements (abdominal and waist circumference)

³ Cardiovascular risk factors: arterial hypertension, tobacco, alcohol abuse, physical activity, diabetes

⁴ Measurement of the systolic blood pressure at D0 W48 W96 according to the recommendations (Pickering et al. Circulation 2005, in Appendix A7)

⁵ Only for women of childbearing potential

⁶ Only in case of suspicion

⁷ Plasma viral loads using a routine technique with a positivity threshold of maximum 50 copies/mL

⁸ If HIV-RNA plasma viral loads > 50 copies/mL an additional blood collection have to be performed, within an interval of two to four weeks, to confirm the virological rebound. If the virological failure is confirmed, a resistance genotype and a dosage of ARV drugs concentration in plasma will be performed on the second HIV-RNA plasma VL test. A plasma bank should also be done

⁹ Urine analysis: proteinuria, albuminuria, creatininuria, glycosuria

¹⁰ Lipid profile: fasting triglycerides, total cholesterol, HDL-cholesterol, LDL-cholesterol

¹¹ DXA-scan sub-study: evolution of the Bone Mineral Density (BMD) and of the body fat distribution in 80 patients

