9.1 Primary Endpoint

Proportion of patients remaining, at week 48, on virological success defined as the absence of 2 consecutive HIV-RNA plasma VL > 50 copies/mL within 2 to 4 weeks.

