16.2.2 Statistical methods

The primary endpoint is the virological success up to week 48 defined by the absence of 2 consecutive HIV-RNA plasma VL > 50 copies/mL within 2 to 4 weeks.

The therapeutic success is defined by the absence of virological failure and the absence of treatment interruption due to adverse event judged by DSMB as related to the trial treatment or procedure up to week 96.

In particular:

- Patients with 2 or more consecutive missing HIV-1 RNA plasma viral load values or lost to follow up will be considered as patients with treatment failure (failing patients).
- Patients who discontinue the treatment due to adverse event judged by DSMB as related to the trial treatment or procedure will be considered as failing patients.
- Patients who discontinued the treatment due to adverse event judged by DSMB as NOT related to the trial treatment or procedure will not be considered as failing patients.
- Patients who gave up will not be considered as failing patients.
- Patients who discontinued the trial treatment for any reason other than a virological failure or adverse event judged by DSMB as related to the trial treatment will not be considered as failing patients.
- Patients with a missing HIV-1 RNA value between 2 documented HIV-1 RNA plasma viral loads \leq 50 copies/mL will not be considered as failing patients.

Analysis of the primary endpoint will be performed on both ITT and per protocol populations. The 95% two-sided confidence interval of the percentage of patients in therapeutic success will be calculated and raltegravir/etravirine will be considered as an acceptable strategy if the lower bound is greater than 90%.

The changes in continuous endpoints will be compared in the ITT population (LOCF or other imputation method to be defined in the statistical analysis plan) using a two-sided non-parametric paired Wilcoxon test with a 5 % type I error. We will use percentage and 95 % two-sided confidence interval to describe the qualitative endpoints, their change over time will be tested a McNemar test with a 5 % type I error.

The adverse events leading to a trial treatment discontinuation and the number of patients who discontinued the trial treatment, as well as the number and nature of grade 3 and 4 adverse events will be described.

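### The primary endpoint makes the 2-to-4-week retest window part of the failure definition, so rebounds confirmed outside it, and some unconfirmed ones, can go uncounted in the regimen's favour

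*Combined protocol and SAP*

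**What the plan says.** The interval appears in the definition of failure as well as in the retest instruction. Section 11.11.1 reads "A virological failure is defined as two consecutive HIV-RNA plasma viral loads > 50 copies/mL within an interval of two to four weeks", and the primary endpoint in section 9.1 is success defined as "the absence of 2 consecutive HIV-RNA plasma VL > 50 copies/mL within 2 to 4 weeks". Sections 16.1 and 16.2.2 repeat it. The French synopsis (section 2) is stricter still: "mesurées dans un intervalle de 2 à 4 semaines maximum".

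The retest itself is mandatory. A footnote to the schedule in section 4 says "If HIV-RNA plasma viral loads > 50 copies/mL an additional blood collection have to be performed, within an interval of two to four weeks". Routine visits are far apart: section 11.5 says "9 visits are scheduled in the clinical centres, W2, W4, W12, W24, W36, W48, W64, W80 and W96", and the schedule shows no viral load at W2.

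Section 16.2.2 then lists special cases. One rule reads: "2 or more consecutive missing HIV-1 RNA plasma viral load values or lost to follow up will be considered as patients with treatment failure". A single gap is excused in one situation only: "Patients with a missing HIV-1 RNA value between 2 documented HIV-1 RNA plasma viral loads", both at or below 50 copies/mL. Patients who give up are not failing. Nor are those who stop for a reason other than virological failure or an adverse event that the DSMB judges related. Section 16.2.1 removes from the per-protocol set anyone who stopped without one of those two events.

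**The concern.** A timing rule meant for sites has become a condition for counting an event. A patient whose second value above 50 arrives at week 5 after the first has rebounded and been confirmed, but does not meet the definition. Nothing else in the plan tells the analyst to count that patient as a failure.

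The other rules make this worse. In section 11.11.1 the action that follows a confirmed rebound turns on the second test and does not repeat the interval. Such a patient can therefore leave trial treatment because of the rebound and still not be a virological failure by definition. Section 16.2.2 then counts the patient as not failing in the ITT analysis, and section 16.2.1 drops the patient from the per-protocol analysis, so neither analysis of the primary endpoint shows the rebound.

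Some unconfirmed rebounds are also left without a rule or counted as not failing. At stake is a decision that allows at most 8 failures in 160.

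**Working it through.** **1. Can scheduled visits produce a failure?** Viral loads are due at D0, W4, W12, W24, W36, W48, W64, W80 and W96. The gaps are 4, 8, 12, 12, 12, 16, 16 and 16 weeks. The only scheduled pair within 4 weeks is D0-W4, and D0 precedes trial treatment. From W4 on, two consecutive scheduled values above 50 (say W36 and W48) cannot meet the definition. Only an unscheduled retest drawn on time can.

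**2. How each kind of rebound is classified (sections 9.1, 16.2.1, 16.2.2).**

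| Course after a value above 50 | Result under the text |
|---|---|
| Second value above 50 at 2-4 weeks | Failure |
| Second value above 50 before 2 or after 4 weeks | Does not meet the definition; if treatment stops, not failing in ITT and out of per-protocol |
| Only the retest missed | No rule: one missing value is not a failure, and the excuse covers only gaps between two values at or below 50 |
| Gives up before retest | Not failing |
| Stops for another reason before retest | Not failing |
| Value above 50 at W48, retest after W48 or absent | No rule |
| Lost to follow-up, or two or more consecutive values missing | Failing, if the section 16.2.2 list governs the primary endpoint |

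The condition in the last row matters. The list follows the definition of therapeutic success up to W96. The next paragraph turns to the primary endpoint, but its confidence interval is for therapeutic success. The text does not settle which endpoint the list serves.

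**3. The plan's own decision rule.** Sections 1 and 16.1: n = 160, accept with at least 152 successes, 95 % probability of discarding efficacy below 90 %, 80 % power at 95 %. With X failures distributed Bin(160, q), P(X ≤ 8) is 0.0174 at q = 0.10 and 0.593 at q = 0.05. The exact type I error is thus 1.7 % and the exact power 59.3 %. The shortfall from 80 % is a separate matter and does not bear on this point. The cut-off itself agrees with the criterion in 16.2.2 under an exact interval.

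**4. Sensitivity to one patient.** The Clopper-Pearson lower bound is the 2.5 % quantile of Beta(x, n − x + 1).
- x = 152 (8 failures): Beta(152, 9), 0.9039, accept.
- x = 151 (9 failures): Beta(151, 10), 0.8959, do not accept.

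Wilson bounds (0.9044 and 0.8966) give the same decisions. The plan does not name its interval method. A Wald bound would pass 151 (0.908), but the stated limit of 8 failures would not.

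**5. Effect of leakage.** Let m be the share of true failures that escape the window and are counted as success. The documents give no value for m. At 90 % true success the observed failure rate is q = 0.10 × (1 − m), and acceptance has probability P(X ≤ 8).

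| m (assumed) | q | P(accept) |
|---|---|---|
| 0 | 0.10 | 1.7 % |
| 10 % | 0.09 | 4.4 % |
| 20 % | 0.08 | 10.0 % |
| 30 % | 0.07 | 20.5 % |

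With 160 × 0.10 = 16 expected failures, a share of 10 to 20 % is 1.6 to 3.2 patients.

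**The case against.** The interval could be read as the retest schedule alone, since the action rule in 11.11.1 asks only whether the second test confirms the rebound. No sentence says that an off-window confirmation is a success, and section 16.2.3 defers a detailed analysis plan in which visit windows could be handled. The safeguards are substantial: the retest is compulsory, breaches touching the primary criterion are major deviations that must be listed (11.10), endpoint data are fully checked (15.2.4), results reach the methodology centre within 10 days (section 20), and people with irregular follow-up are not enrolled (8.2). The leakage share has no source, and at 10 % the 4.4 % stays within the stated 5 %. A one-patient flip is a feature of any sharp cut-off.

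Much of this stands. Off-window cases should be few, and the share is only an assumption. But the safeguards make such cases rarer and visible; they do not classify them. The endpoint sections state the interval inside the definition, so an analyst who follows the text has no basis for counting a late confirmation. Deferral to a later plan is a reason to settle the rule there, not evidence that it has been settled.

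A reader might infer that every rebound never retested counts as success. The documents do not support that. Section 16.2.2 makes loss to follow-up and two or more consecutive missing values failures, provided that the list applies to the primary endpoint.

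**Conclusion.** The point holds for off-window confirmations, which fall outside the failure definition as written. It also holds for a narrower set of unconfirmed rebounds: only the retest missed, giving up or stopping for another reason before retest, and a rebound at W48. These are unclassified or counted as not failing. The misclassification runs one way, from failure to success.

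Its size depends on how many retests fall outside the window, which the documents do not report. One patient is enough to move the exact lower bound from 89.6 % to 90.4 %. With an assumed 10 to 20 % of true failures escaping, the chance of accepting a regimen with 90 % true success is 4.4 to 10.0 % instead of 1.7 %. The lower figure stays inside the design's stated 5 %, though above the 2.5 % per side that a two-sided 95 % interval implies. It would be too strong to say that the type I error is inflated beyond the stated level; that follows only towards the upper end of the assumed range. This should be corrected, and wording alone can do it.

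**What to change.** Leave the site retest procedure and the management rule in section 11.11.1 as they are. Change only how outcomes are classified for analysis, in sections 9.1 and 16.2.2, with matching wording in the synopses and 16.1:

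- Failure for analysis is two consecutive values above 50 copies/mL on separate dates, the first on trial treatment at or before the W48 visit, whether or not the second falls within 2 to 4 weeks. Confirmation may come after W48.
- A last on-treatment value above 50 with no later viral load counts as failure, including in patients who give up.
- State that the missing-data list in 16.2.2 applies to the primary endpoint.
- Report the strict-window definition as a sensitivity analysis, with the number of patients reclassified.

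Appendix A8 shows that first results were already known when version 3.0 was written. If the primary definition can no longer change, report the any-interval count as the sensitivity analysis instead, again with the number reclassified.

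The change needs no extra visits or samples. It may add one or two failures. It may occasionally join two isolated low-level values weeks apart, or let a very early repeat confirm a rebound, and it counts some unconfirmed last values as failures. The strict-window analysis shows how much these cases matter.
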